9.1.6 STUDY EXIT

A Study Exit CRF must be completed for any subject who signed an informed consent form, as they are considered enrolled in the study. Data to be collected at this visit includes:

- Record paresthesia and pain map for current arm
- Record pain rating for current arm
- Record program preference

- Record satisfaction and pain relief from each program
- Study exit date and reason for study exit

Additional data that will be collected as they occur include:

- Device or procedure related AEs
- Technical Observations/Device Deficiencies
- Surgical Interventions

The following scenarios may lead to study exit and will require completion of a Study Exit CRF.

- Inclusion/exclusion criteria not met
- Subject ineligibility for implant, in the opinion of the study physician
- SCS lead removal without re-implantation
- Implant attempted, however no SCS was implanted
- Voluntary withdrawal by subject
- Investigator chooses to withdraw a subject
- Failure to maintain adequate study compliance
- Subject Death

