- Compare the change from baseline of pain scores between the two study arms. Pain scores are obtained using the Numeric Rating Score (NRS) administered at baseline and after completion of each arm of the study.
- Paresthesia distribution: At end of each arm, subjects will be asked to complete a diagram that shows distribution of paresthesia.
- At the end of the trial period, subjects will be asked to select their favorite program.
- At the end of the trial period, subjects will be asked to rate the quality of the pain relief achieved during the trial (from either arm) using the following scale; *Excellent, Very Good, Good, Fair or Poor*.
- At the end of the trial period, subjects will be asked to rate their overall satisfaction with the pain relief achieved during the trial (from either arm) using the following scale: *Very Satisfied, Satisfied, Neither Satisfied nor Unsatisfied, Unsatisfied, or Very Unsatisfied*.

Secondary Safety Objectives Secondary measures of therapy safety will include:

- Rate of device-related and/or procedure-related AEs from the Trial procedure through study completion.

Study Procedures After the subject has consented to the study, he or she will be enrolled in the clinical study and undergo a baseline evaluation. The patient will then be randomly assigned to arm one (pulse width <500 μ sec) or arm two (pulse width >1000 μ sec) and undergo an Algovita® trial procedures. Following the trial procedure, the subject's EPG will be set to the appropriate pulse width, based on the arm assigned, and then programmed to achieve optimal pain relief. For the next three days, the subject will evaluate pain relief generated by the 1st assigned program (arms).

After 3 days, the patient will visit the Ohio Pain Clinic for data collection and then reprogramming of the EPG for the next arm. For the next three days, the subject will evaluate the SCS therapy generated by the 2nd assigned program and then return to the clinic for data collection, removal of the leads and exit from the study. After the subject is exited from the study, he or she will be followed by the Ohio Pain Clinic per usual care. The data collection requirements are listed below.

Enrollment:

- Informed consent signed
- Confirmation of study eligibility

Baseline evaluation:

- Record pain ratings and pain map
- Relevant medical history
- Physical examination
- Brief Pain Inventory
- Demographics

After the lead implantation:

- Implant procedure

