2.2 Secondary Objectives

Secondary measures of therapy effectiveness will include:

1. To evaluate the effect of conventional pulse widths <500 μ sec and pulse widths >1000 μ sec on clinical outcomes during temporary trial as measured by the percent reduction in targeted pain compared to baseline using the NRS at the end of the trial period.
2. At end of each arm, subjects will be asked to complete a diagram that shows distribution of paresthesia.
3. At the end of the trial period, subjects will be asked to select their favorite program.
4. At the end of the trial period, subjects will be asked to rate the quality of the pain relief achieved during the trial (from either arm) using the following scale; *Excellent, Very Good, Good, Fair or Poor*
5. At the end of the trial period, subjects will be asked to rate their overall satisfaction with the pain relief achieved during the trial (from either arm) using the following scale; *Very Satisfied, Satisfied, Neither Satisfied nor Unsatisfied, Unsatisfied or Very Unsatisfied*
6. Number of patients who achieved $\geq 50\%$ pain relief during the trial (from either arm)
7. Rate of device-related and/or procedure-related AEs from SCS implant through study completion or study exit.

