4.1 OVERVIEW OF DATA COLLECTION AT STUDY VISITS

Assessments and Data Collection	Enrollment	Baseline	After Implant	Follow-up Visits	Study Exit
• Eligibility confirmation	✓				
• Medical history		✓			
• Physical exam	✓				
• Informed consent	✓				
• Record demographics		✓			
• Brief Pain Inventory		✓			
• Record pain map		✓			
• Implant and system information			✓		
• Record paresthesia and pain map for current arm			✓	✓	✓
• Record pain rating for current arm	✓	✓	✓	✓	✓
• Document any AEs	✓	✓	✓	✓	✓
• Record subject program preference					✓
• Record subject satisfaction and pain relief from each program					✓
• Document study exit reason & any AEs					✓

Figure 4.1 Study Flowchart

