5.2 SECONDARY ENDPOINTS

Endpoints for secondary measures of therapy effectiveness:

- To evaluate the effect of conventional pulse widths and pulse widths $>1000\mu\text{sec}$ clinical outcomes during temporary trial as measured by the percent reduction in targeted pain compared to baseline using the NRS at the end of the trial period.
- Comparison of paresthesia overlap of pain between each arm as evaluated by the reviewer to determine which arm had superior pain overlap (coverage)
- Patient *preference* for pulse widths $>1000\mu\text{sec}$ or $<500\mu\text{S}$
- Patient *satisfaction* for pulse widths $>1000\mu\text{sec}$ or $<500\mu\text{S}$
- Number of patients who achieved $\geq 50\%$ pain relief during the trial (from either arm)
- Rate of device-related and/or procedure-related AEs from Trial Lead implant through study completion.

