9.1.5 FOLLOW-UP VISITS

Follow-up visits will occur at day 4 and 7 (+/-2) post-implantation. Data collected at these visits will be recorded on case forms (CRFs) and will include:

- Record paresthesia and pain map for current arm
- Record pain rating for current arm
- Document AEs
- Program subject with next arm parameters and document

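### Per-program satisfaction and rated pain relief are collected only at Study Exit, so the first program is rated from recall and the second concurrently, although the day-4 visit could capture the first

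*Combined protocol and SAP*

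**What the plan says.** - **Endpoint.** Section 5.2 lists "Patient *satisfaction* for pulse widths" above 1000 or below 500 μsec among the secondary endpoints, so each rating must be attributable to one program.
- **When it is collected.** Section 9.1.6 lists "Record satisfaction and pain relief from each program" under Study Exit. The table in section 4.1 has the row "Record subject satisfaction and pain relief from each program", ticked only in the Study Exit column. The synopsis schedule and the table in section 9.1.1 show the same.
- **Visits.** Section 9.1.5: "Follow-up visits will occur at day 4 and 7 (+/-2) post-implantation". The items there include "Record pain rating for current arm", with maps, adverse events and reprogramming, but no satisfaction or relief rating.
- **Sequence.** Synopsis, Study Procedures: "After 3 days, the patient will visit the Ohio Pain Clinic for data collection and then reprogramming of the EPG for the next arm". Then: "For the next three days, the subject will evaluate the SCS therapy generated by the 2nd assigned program", followed by the return visit and exit.
- **Objectives.** Section 2.2, item 5, asks subjects at the end of the trial period to "rate their overall satisfaction with the pain relief achieved during the trial (from either arm"). Item 4 asks for quality of relief in the same way. Both read as one overall rating, not one per program.

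**The concern.** In a crossover, the within-subject difference is informative when both conditions are measured in the same way. Here one rating is concurrent. The other is recalled after the program has been replaced and the subject has tried its competitor. Both are given at the visit that records the preferred program, so subjects may adjust the ratings to agree with their choice, and satisfaction may then add little to the preference endpoint.

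The schedule does not force this. A visit already takes place at the end of the first program, data are collected there before the switch, and the plan uses it for the NRS and the maps. Preference is a comparison and has to wait until both programs have been tried; a rating of one program does not.

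**Working it through.** The plan gives no figure for this point, so there is none to reproduce. The check has two parts.

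**1. Recall interval**

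- Inputs: follow-up at days 4 and 7 (section 9.1.5); second program of three days (synopsis, Study Procedures).
- First program: 7 − 4 = 3 days between switch-off and rating, which agrees with the three-day second period.
- Second program: 0 days.
- If the ±2-day window applies to both visits, the windows alone would allow up to 9 − 2 = 7 days for the first program.
- If the first program is rated at day 4 before reprogramming, its interval falls from 3 days to 0.

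**2. Effect on the pulse-width comparison**

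Assume that the most recent program gains d points on the 5-point satisfaction scale. The documents give no value for d, so a range is shown. Let p be the share of subjects in one order.

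- Each within-subject difference shifts by +d or −d according to order.
- Mean shift = d·p − d·(1 − p) = d(2p − 1).
- Added variance of the differences = d² − d²(2p − 1)² = 4p(1 − p)d², which is d² when the orders are balanced.
- With a fair random order, E(p) = 0.5, so the expected mean shift is zero.
- No balancing rule is stated. Taking simple randomization as an assumption, for even n the average size of the chance imbalance is E|2p − 1| = C(n, n/2)/2ⁿ.

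The sizes 50 and 100 come from section 4.0; section 8.3 also caps the study at 100. E|2p − 1| is 0.112 at n = 50 and 0.080 at n = 100.

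| Assumed d | Mean absolute shift, n = 50 | Mean absolute shift, n = 100 | Added variance (balanced) |
|---|---|---|---|
| 0.25 | 0.112 × 0.25 = 0.03 | 0.080 × 0.25 = 0.02 | 0.0625 |
| 0.5 | 0.112 × 0.5 = 0.06 | 0.080 × 0.5 = 0.04 | 0.25 |
| 1.0 | 0.112 × 1.0 = 0.11 | 0.080 × 1.0 = 0.08 | 1.0 |

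A lopsided split is unlikely at these sizes. The probability of 7:3 or worse is 0.0066 at n = 50 and 0.00008 at n = 100. In a group of 10 it is 2 × (120 + 45 + 10 + 1)/1024 = 0.344, and a 7:3 split gives a shift of 0.4d, or 0.2 points at d = 0.5.

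**The case against.** **Randomized order already protects the comparison.** This stands as far as expected bias goes. A reader might infer that exit-only rating favours one pulse width; the documents do not support that, because order is assigned at random. A period term in the analysis could also absorb the average recency shift and the variance it adds. Section 11 specifies no such term and no effectiveness analysis for these ratings, but that is a separate gap. A period term would not remove individual recall error or ratings made to agree with the stated preference.

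**The 34% chance of a 7:3 split sounds alarming.** It applies to 10 subjects. The synopsis gives 10 as a per-site number, and no analysis of satisfaction by site is planned. Section 8.0 does speak of up to 10 subjects undergoing the trial, which conflicts with the 50 to 100 in section 4.0; only if 10 were the whole study would the figure apply.

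**Subjects who leave during the second program would have no rating of the first.** A reader might infer this, but section 9.1.6 requires an exit form for everyone who signed consent, and its data list includes this item. Only subjects who cannot be assessed at exit would lack it.

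**Pain relief is measured per arm anyway.** This is correct for the NRS, and hence for percent reduction and the count with at least 50% relief when derived from the per-arm records. It also holds for the maps, including the primary endpoint. Only the subjective ratings are affected, and section 5.2 does not list quality of relief as an endpoint.

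**Rating both programs at exit gives one common frame of reference.** This is a fair argument for a comparative question, and preference already serves that purpose. A day-4 rating has no comparator and is closer to the implant procedure, and the second rating still follows experience of the first. The change therefore removes recall and retrospective contrast from the first rating only.

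**Conclusion.** The point holds as an avoidable measurement asymmetry in a secondary, subjective outcome. The first program is rated about 3 days late and from memory; the second is rated with no delay. The tables and the visit text agree on this, so it is not a gap in one table.

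Its size is modest. Expected bias is zero. For an assumed d of 0.5 points, the chance shift averages about 0.06 points at n = 50 and 0.04 at n = 100, and the variance of the within-subject differences rises by 0.25. These figures rest on an assumed d, equal for both pulse widths, and on simple randomization; blocked allocation would bring the chance shift close to zero but leave the added variance. Individual recall error is additional and cannot be sized from the documents.

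The change is still worth making, because concurrent first-program ratings cannot be recovered afterwards. The wording must be settled in any case: the objectives describe one overall rating covering both arms, the schedules say one per program, and a single overall rating cannot support the endpoint in section 5.2. The draft case report forms, which might show the intent, are not among the documents reviewed.

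**What to change.** 1. In section 9.1.5, the synopsis visit list and all three schedule tables, add at the day-4 visit: *record satisfaction and quality of pain relief for the current program, before any reprogramming*.
2. Record the same two items for the second program at the end of that program.
3. Define the satisfaction endpoint in section 5.2 from these two ratings.
4. Keep program preference, and the overall end-of-trial ratings in section 2.2 (items 4 and 5) and the synopsis, at Study Exit as separate items. Replacing them with a rating of the second program alone would remove the data for two stated objectives.
5. Reconcile the wording so that it is clear which ratings are overall and which are per program.

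Cost: a wording change to the protocol and case report form, two short questions and about a minute of patient time at a visit that already takes place, with no added visit or staff. The second program's rating will still follow experience of the first, so order effects are reduced but not eliminated. No sample size or power figure changes.

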10.0 ADVERSE EVENT REPORTING

10.1 ADVERSE EVENTS

At each evaluation, the investigator will determine whether any adverse events (AE's) have occurred. For the purpose of this protocol, an adverse event is any undesirable clinical occurrence in a subject that can be attributed to the device or incision closure procedure.

In this study, patients should be encouraged to report AE's spontaneously or in response to general, non-directed questioning (e.g., "How has your health been since the last visit?"). Any time during the study, the patient may volunteer information that resembles an AE. If it is determined that an AE has occurred, the investigator should obtain all the information required to complete the AE Form of the CRF.

The following categories of adverse event severity are to be used:

Mild	Awareness of a sign or symptom that does not interfere with the patient's usual activity or is transient, resolved without treatment and with no sequelae
Moderate	Interferes with the patient's usual activity
Severe	Any fatal or immediately life-threatening clinical experience that requires a subject to be hospitalized, or hospitalization is unduly prolonged because of potential disability or danger to life or because an intervention has been necessitated. This includes events that cause fetal distress, fetal death, congenital abnormality or malignancy or any permanently disabling event.

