4.0 STUDY DESIGN

The proposed study is a prospective, single-center, two arm, randomized, crossover design to be conducted at The Ohio Pain Clinic. The study will enroll up to 100 subjects in order to assure at least 50 subjects in the study. Subjects selected to participate in the trial have back and/or leg pain, have been identified as a candidate for SCS and have agreed to undergo a temporary SCS trial using the Algovita® system with percutaneous leads. Each subject will be followed during the trial period of approximately 7 days.

The study will end when the last subject has completed the trial period or is exited. The expected enrollment period for this study is approximately three months. After exit from the clinical study, subjects will continue to be followed by their physician per usual care. All device and procedure-related AEs will be collected and reported per the study protocol.

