10.2 ANTICIPATED ADVERSE DEVICE EFFECTS

The following ANTICIPATED EVENTS have been identified as possible complications of implanting neurostimulator leads.

- Infection at implant site
- Pain at implant site
- Bleeding
- Bruising
- Device failure
 - Unintended stimulation
 - Increased stimulation
 - Decreased stimulation
 - Lead breakage/migration
 - Battery depletion
 - Erosion of device
 - General device failure

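### Section 10.1 limits procedure-caused adverse events to an incision closure procedure that the protocol does not describe, so the recording definition is narrower than the safety endpoint it feeds

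*Combined protocol and SAP*

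**What the plan says.** Section 10.1 sets the definition for the whole protocol: "an adverse event is any undesirable clinical occurrence in a subject that can be attributed to the device or incision closure procedure". It then ties recording to that definition. Once an AE is determined to have occurred, "the investigator should obtain all the information required to complete the AE Form of the CRF".

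The safety endpoint is worded three times, each time without mention of incision closure:

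- Synopsis, Secondary Safety Objectives: "Rate of device-related and/or procedure-related AEs from the Trial procedure through study completion"
- Section 2.2, item 7: "Rate of device-related and/or procedure-related AEs from SCS implant through study completion or study exit"
- Section 5.2: "Rate of device-related and/or procedure-related AEs from Trial Lead implant through study completion"

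Section 9.1.6 lists, among data to be gathered as they arise, "Device or procedure related AEs". Section 4.0 and the synopsis share a general commitment: "All device and procedure-related AEs will be collected and reported per the study protocol".

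Section 10.2 introduces its list of anticipated device effects as events that "have been identified as possible complications of implanting neurostimulator leads".

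**The concern.** The definition has two limbs: the device, and one named procedure. The named procedure does not belong to anything the protocol describes. The study uses percutaneous trial leads, which are placed at the start and taken out at the end. An investigator who applies 10.1 as written would have no ground to call an event an AE if it arose from placing or removing the leads and was not put down to the device. An investigator who works from 9.1.6 would record the same event.

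At stake is whether the only safety endpoint in the plan is collected under a definition that covers what it is meant to count, and whether all investigators record by the same rule.

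**Working it through.** The plan gives no figure on this point and no arithmetic applies. The check is a comparison of texts.

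**Step 1. Which text governs recording?** Section 10.1 offers its definition for this protocol and makes the AE Form follow from it. Section 9.1.5 and the visit schedules ask for AEs to be documented but define nothing, so they take their meaning from 10.1.

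**Step 2. Is there an incision closure procedure?** The term occurs nowhere else in the available text. Section 9.1.4 describes the trial lead implant. The synopsis (Study Procedures) describes lead removal at the last visit. One part of the document, between Section 13.8 and the Declaration of Helsinki, was not available. The contents list puts the signature page there, so it is unlikely to define the term.

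**Step 3. What must the endpoint count?** Set side by side:

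| Place | Procedure covered |
|---|---|
| 10.1 (definition, leads to AE Form) | Incision closure only |
| Synopsis, safety objective | Procedure-related, counted from the trial procedure |
| 2.2, item 7 | Procedure-related, counted from SCS implant |
| 5.2 | Procedure-related, counted from trial lead implant |
| 9.1.6 | Procedure-related, as they occur |

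All three endpoint wordings start the count at the implant of the leads. That points to the lead procedure and not to closing an incision.

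**Step 4. Which statements conflict firmly with 10.1?** The endpoint and the 9.1.6 list do. The shared sentence in the synopsis and Section 4.0 is weaker evidence: it promises collection in accordance with the protocol, which can be read as deferring to 10.1. I do not rely on it.

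**Step 5. What falls in the gap?** An event is in the gap if it was caused by lead placement or lead removal, is not attributed by the investigator to the device, and did not come from closing an incision. It is outside 10.1 and inside 5.2. Section 10.2 narrows the gap, because it treats implant-site infection and pain, bleeding and bruising as device effects. Its list is introduced as complications of implanting leads, says nothing of removal, and does not change the definition.

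**The case against.** The strongest reply is that the protocol plainly intends to collect procedural events and gives several routes for doing so. Section 9.1.6 asks for them directly, and for surgical interventions as well. Section 9.1.4 puts procedure data on an Implant CRF. Section 10.2 classes the common lead-implant complications as device effects, which brings them under the device limb of 10.1. Section 11.2 compares complications, a word not tied to 10.1, and tabulates relationship to the treatment procedure. The odd phrase may simply be carried over from another protocol: Section 13.5 refers to a different device and a different condition. That origin is an inference, and the point does not need it.

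Much of this stands, and it makes the practical gap small. It does not remove the inconsistency, because none of these sections amends the definition that leads to the AE Form. Section 10.3 is only a partial backstop: it concerns unanticipated serious effects associated with a device, and its reporting table has rows for deaths and device effects but none for procedure-related events.

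It could also be said that the endpoint borrows the 10.1 meaning of an AE, so nothing conflicts. Then the endpoint's procedure-related part would refer only to a procedure the protocol does not describe, while its count begins at lead implant. The text needs repair on that reading too.

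In the other direction, a reader might infer that procedural events will be lost and the reported safety rate biased downward. The documents do not support that. They show a definition that permits omission, not one that will cause it, and 9.1.6 pulls the other way.

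**Conclusion.** Section 10.1 is wrong as written and inconsistent with the safety endpoint and with Section 9.1.6. Severity is low. What can be left out is limited to events of lead placement or removal that the investigator does not attribute to the device.

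I put no percentage on the effect. The documents give no expected number of such events, and it may be zero. They also disagree on how many subjects will be treated: Section 4.0 speaks of up to 100 enrolled and at least 50 in the study, while Section 8.0 speaks of up to 10 undergoing the trial, which may or may not be a per-site figure. The primary comparison of pain maps is unaffected.

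The conclusion rests on a literal reading of 10.1 and on the absence of any incision closure procedure from the available text. Confidence is high for the mismatch in wording; it does not extend to how many events are affected. The draft CRFs are in Appendix 17, which was not available, so no defect in the AE Form itself is claimed.

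**What to change.** In Section 10.1, replace the reference to the device or incision closure procedure with: *the device or a study procedure (trial lead placement or trial lead removal)*. Naming the two procedures separately makes clear that relatedness means cause, and keeps the phrase from being read as the whole stimulation period. The recording definition then matches Sections 2.2, 5.2 and 9.1.6.

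Check that the AE Form in Appendix 17 lets the investigator record relationship to the device, to lead placement and to lead removal.

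The cost is one phrase and one form check. The reported AE rate may come out slightly higher, because events that the present wording permits to be left out would be recorded.

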Multi-Center Evaluation of Clinical Outcomes of Pulse Widths <500 μ sec and >1000 μ sec During a Temporary Spinal Cord Stimulation Trial

Title: Multi-Center Evaluation of Clinical Outcomes of Pulse Widths <500 μ sec and >1000 μ sec During a Temporary Spinal Cord Stimulation Trial

Protocol Number: TBD

Device: Nuvectra® Algovita® Spinal Cord Stimulation System

Sponsor: The Ohio Pain Clinic
[name]
[name]

Sponsor Contact: [name]
[name]
[name]
[contact]

Study Sites: TBD

Medical Monitor: [name]
Ohio Pain Clinic
[name]
[name]

Date of Protocol: TBD

Confidentiality Statement

The confidential information in this document is provided to you as an investigator or consultant for review by you, your staff, and the applicable Institutional Review Board. Your acceptance of this document constitutes agreement that you will not disclose the information contained herein to others without written authorization from .

Protocol Synopsis

Sponsor Contact Information Ohio Pain Clinic
[name]
[name]
[name]

Study Purpose The purpose of this study is to evaluate the effect of pulse widths <500 μ sec and >1000 μ sec on clinical outcomes during a temporary SCS trial.

Study Design and Scope The proposed study is a prospective, multi-center, two-arm, randomized, crossover design to be conducted at up to 10 sites. The study will enroll up to 100 subjects in order to include up to 10 subjects in the study per site. Subjects selected to participate in the trial have back and/or leg pain, have been evaluated as a candidate for SCS and have agreed to undergo a temporary SCS trial using the Algovita® system with percutaneous leads. Each subject will be followed during the trial period of approximately 7+-2 days. The study will end when the last subject has completed the trial period and exited. The expected enrollment period for this study is approximately six months. After exit from the clinical study, subjects will continue to be followed by their physician per usual care. All device and procedure-related AEs will be collected and reported per the study protocol.

Primary Effectiveness Objective Compare the change in the patient defined pain coverage map from baseline to the end of the 7+-2 day trial.

Secondary Effectiveness Objectives Secondary measures of therapy effectiveness will include:

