11.2 Safety Analysis

All patients who received treatment will be included in the safety analysis. The proportion of patients with complications will be compared by Fisher's Exact test. The two treatment groups will be compared using t-test for continuous variables and chi square test for category variables. All adverse events will be listed and the frequencies, severity, and relationship to the treatment procedure will be tabulated and compared by treatment groups.

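### Section 10.1 makes attribution part of the adverse event definition, so the planned data have no all-cause count with which to check attribution between pulse-width programs

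*Combined protocol and SAP*

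**What the plan says.** Section 10.1 gives the investigator the decision: "At each evaluation, the investigator will determine whether any adverse events (AE's) have occurred". The definition applied covers "any undesirable clinical occurrence in a subject that can be attributed to the device"; incision closure is the only other source it names. Complaints are invited by open, general questioning, but the form depends on the decision: "If it is determined that an AE has occurred, the investigator should obtain all the information required to complete the AE Form". No form or log is described for complaints judged unrelated.

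The collection scope elsewhere matches this. The synopsis and section 4.0 both state: "All device and procedure-related AEs will be collected and reported per the study protocol". Section 9.1.6 lists "Device or procedure related AEs" among the data gathered as they occur. The safety endpoint in section 5.2 is the rate of AEs related to the device, the procedure or both.

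Two places do not fit. Section 11.2 says that frequency, severity and "relationship to the treatment procedure will be tabulated and compared by treatment groups", without defining a relationship scale. The section 4.1 schedule ticks AE documentation at enrollment and baseline, before any lead is placed.

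**The concern.** If relationship is a variable to be compared between groups, it has to be recorded on events that were not first selected on it. Here the selection comes first. Whatever drives the investigator's readiness to attribute an event also drives whether the event enters the data.

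This matters because the safety endpoint is itself a rate of related events, compared between two programs in the same patients. If attribution were more ready under one pulse width, the recorded rates would differ without any difference in what patients experienced, or a real difference could be masked. The planned AE data could not tell these situations apart, and the missing forms could not be fully reconstructed afterwards.

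**Working it through.** The documents state no AE rate, attribution rate, alpha or power, so there is no figure of the plan's own to reproduce. The check is first textual, then an illustration on assumed values.

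**1. Which rows the relationship table can have.** Section 10.1 admits an event if it can be attributed to the device or to the procedure. Section 11.2 classifies by relationship to the treatment procedure. An event attributed to the device alone could appear as not procedure-related, so relationship can vary among recorded events. The row that cannot exist is unrelated to both.

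**2. Whether the assessor knows the program.** Section 6.0 lists screening, demographics, training and adherence to the plan as its measures against bias. It names neither masking nor independent adjudication. Section 9.1.4 has programming done at the investigator's direction, and section 9.1.5 puts AE documentation and reprogramming at the same visit. Knowledge of the program is a reasonable inference, but it is not stated.

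**3. What is observed.** For each program:

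recorded rate = (rate of all undesirable occurrences) × (probability that an occurrence is attributed)

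Only the product is observed. With equal all-cause rates, the ratio of recorded rates equals the ratio of attribution probabilities, whatever the common rate.

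**4. Illustration (all rates assumed).** With 10% under each program and attribution of 0.5 and 0.8: 0.10 × 0.5 = 5%, 0.10 × 0.8 = 8%, and 8/5 = 1.6. Half of the events go unrecorded under one program and 20% under the other.

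The next table gives a wider range. Its last two columns are the chance of declaring a false difference (two-sided 5%, unpaired approximation) with 50 or 100 observations per program.

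| All-cause rate, both programs | Attribution | Recorded rates | Ratio | 50 per program | 100 per program |
|---|---|---|---|---|---|
| 20% | 0.5 / 0.7 | 10% / 14% | 1.4 | 8.9% | 13.7% |
| 20% | 0.5 / 0.9 | 10% / 18% | 1.8 | 20.8% | 37.0% |
| 40% | 0.5 / 0.7 | 20% / 28% | 1.4 | 15.2% | 26.2% |
| 40% | 0.5 / 0.9 | 20% / 36% | 1.8 | 42.8% | 71.5% |

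With equal attribution of 0.5 the recorded rates are equal (10% each or 20% each). Section 11.2 names Fisher's exact test. At the expected counts it gives p below 0.05 only in the most extreme case (40%, 0.5 / 0.9, 100 per program: p = 0.018). The main consequence is therefore a distorted estimate, and a false significant result is secondary. The approximation also ignores the pairing in the crossover.

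**5. What all-cause recording would add.** In the first row of the table, the data would show 20% under both programs and a related share of 50% against 70%. Equal totals with unequal shares would point to attribution without proving it, because the share truly caused by stimulation could also differ.

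**6. The schedule.** A newly arising event at enrollment or baseline cannot be attributed to a device or procedure that has not yet been used. The ticks in section 4.1 therefore ask for something the section 10.1 definition excludes.

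**The case against.** The best defense is that related-only collection is a deliberate scope. It is stated in the synopsis, in sections 4.0 and 9.1.6 and in the endpoint. It suits a post-market study of an approved device used within its labeling (section 3.2), with about 7 days of follow-up. That stands: the scope is legitimate and the endpoint need not change.

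A reader might go further than the documents allow, and these limits also stand:

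- **That the section 11.2 table has only one category.** It does not follow, because device and procedure are separate sources.
- **That uncertain events are lost.** The wording covers what can be attributed, which may well include uncertain events. Only those judged unrelated to both are clearly excluded.
- **That differential attribution is undetectable.** Section 10.3 makes death reportable with no condition on relatedness. Section 9.1.6 records surgical interventions and device deficiencies, and section 13.3 gives monitors access to source documents. These offer a partial check outside the AE analysis.
- **That the documents declare the assessor unmasked.** They are silent on this.
- **That the 1.6 ratio is evidence.** It is simply 0.8/0.5, both assumed. Many anticipated events in section 10.2, such as implant-site infection or lead migration, have an evident source, and a large attribution gap for these is unsupported.

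The draft case report forms are also not in the supplied text, so relationship fields may already exist. None of this supplies an all-cause count, and it does not reconcile section 10.1 with the schedule in section 4.1.

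**Conclusion.** The point holds as a cheap improvement to a secondary safety measure. Attribution is a condition for being an AE, the relationship table can have no row for events unrelated to both device and procedure, and the planned AE data cannot show whether attribution differs between programs. The section 4.1 ticks at enrollment and baseline do not fit the definition.

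The size of any bias is unknown. Nothing in the documents shows that attribution does differ by pulse width, and every rate in the illustration is assumed. The concern rests on two readings: that the assessor probably knows the program, and that no log of unrelated events exists outside the text supplied.

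**What to change.** - **Section 10.1:** define an AE as any undesirable clinical occurrence between the trial procedure and study exit, whatever its cause. This also removes the reference to incision closure, which does not match the lead-implant procedure named in the endpoint.
- **AE Form:** record onset date and, as separate fields on a defined scale, relationship to device, to procedure and to stimulation. Check first whether the draft form already has these.
- **Endpoint:** leave it as related AEs, derived from those fields.
- **Section 11.2:** report all-cause and related events by the program in use at onset.
- **Consistency:** align the section 4.1 schedule and the scope statements in the synopsis and sections 4.0 and 9.1.6.

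The cost is a definition change, a few form fields and a few more AE forms per site over about 7 days per subject. The investigator would still judge relatedness, so the change lets differential attribution be checked but does not prevent it. If related-only collection is kept, the least that is needed is to say so openly and to bring section 11.2 and the section 4.1 schedule into line with it.
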